7.2.1.2 Exclusion Criteria

Exclude any subjects duplicated among the different carfilzomib regimens

7.2.2 Matching

The propensity score matching approach for the comparison of outcomes among carfilzomib regimens is detailed in Section 9.5.2.1 of the SAP. Briefly, to generate the propensity score for each subject, all the variables or covariates specified in [List 1](#) will be included in the propensity score model (logistic regression model) with the dosing regimen as the binary response. There will be propensity score matching for the datasets of Kd27 versus Kd56 and for K27 versus Kd27. For the evaluation of these

secondary and exploratory objectives, the propensity score matching creates mutually exclusive sets of observations that have similar propensity scores. The Greedy nearest neighbor 1:1 matching without replacement will be used to sequentially match each subject in the Kd56 regimen with one subject in the Kd27 regimen if the difference in the logits of the propensity score for pairs of subjects from the two groups is less than or equal to 0.1 times the pooled estimate of the standard deviation (Austin, 2014). The threshold 0.1 was chosen so that the resulting matched samples have balanced distributions of baseline covariates. Same method will be used to create a propensity score matched samples for subjects with Kd27 or K27.

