6.3 Exploratory

Compare efficacy and safety outcomes for K27 dosing regimens without and with dexamethasone (K27 versus Kd27)

7. Research Methods

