20140120 (PX-171-005)	Phase 2 Study of the Safety and Pharmacokinetics of carfilzomib in Subjects with relapsed and Refractory Multiple Myeloma and Varying Degrees of Renal Function	Relapsed and refractory MM; ≥ 2 prior tx; varying degrees of renal function	Phase 2, single arm, parallel cohorts by CrCL grouping	PK; safety and tolerability; PDn; QTc; efficacy	Carfilzomib 15/20/27 mg/m ² (2 to 10 min)	K27: 8 subjects Kd27: 20 subjects

Footnotes defined on last page of the table

Table 1. Summary of Individual Clinical Trials to Derive Subject Data for Pooled Analysis

Study Number	Study Title	Subject Population	Design	Objectives	Drug Combination/ K Dose Schedule ^a	Eligible Subjects (K regimen: subject #)
20140119 (PX-171-004 – Part 1 and Part 2)	An Open-label, Single-arm, Phase 2 Study of Carfilzomib in Patients with Relapsed and Refractory Multiple Myeloma	Relapsed or refractory MM; 1 to 3 prior tx	Phase 2 Part 1: single arm Part 2: 2 dosing cohorts	Safety; efficacy; PK	Carfilzomib Part 1: 20 mg/m ² (10 min) Part 2: 20 or 20/27 mg/m ² (10 min) up to 12 cycles	K27: 78 subjects
20140118 (PX-171-003 – Part 1 (A0) and Part 2 (A1))	An Open-label, Single-arm, Phase 2 Study of Carfilzomib in Patients with Relapsed and Refractory Multiple Myeloma	Relapsed and refractory MM; ≥ 2 prior tx	Phase 2, single arm	Efficacy; safety; PK; PDn	Carfilzomib Part 1: 20 mg/m ² (2 min) Part 2: 20/27 mg/m ² (10 min) up to 12 cycles	K27: 200 subjects
20130402 (CFZ002)	An Open-label, Single Arm, Phase 1 Study of the Pharmacokinetics and Safety of Carfilzomib in Subjects with Advanced malignancies and varying Degrees of Hepatic Impairment	Relapsed or progressive advanced malignancies; ≥ 2 prior tx; varying degrees of hepatic function	Phase 1, comparative PK with 4 cohorts based on liver function	Assess hepatic impairment on AUC	Carfilzomib + dexamethasone K 20/27/56 mg/m ² (30 min) dex 8 mg BIW	K56: 2 subjects

Footnotes defined on last page of the table

Table 1. Summary of Individual Clinical Trials to Derive Subject Data for Pooled Analysis

Study Number	Study Title	Subject Population	Design	Objectives	Drug Combination/ K Dose Schedule ^a	Eligible Subjects (K regimen: subject #)

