ALL = acute lymphoblastic leukemia; AUC = area under the concentration-time curve; BIW = twice weekly; BTZ = bortezomib; CFZ = carfilzomib; C-MAP = Carfilzomib Multiple Myeloma Expanded Access Protocol; CrCL = creatinine clearance; CYC = cyclophosphamide; Dara = daratumumab; DDI = drug-drug interaction; DEX = dexamethasone; ESRD = end-stage renal disease; HD = Hodgkin's disease; LEN = lenalidomide; MEL = melphalan; Mito = mitoxantrone; MM = multiple myeloma; MTD = maximum tolerated dose; NHL = non-Hodgkin's lymphoma; PDn = pharmacodynamics; PEG = polyethylene glycol; PK = pharmacokinetics; POM = pomalidomide; PRED = prednisone; QD = once daily; QTc = corrected QT interval; QW = once weekly; R3 = dexamethasone, mitoxantrone, PEG-asparaginase, and vincristine; SCLC = small-cell lung cancer; tx = therapy(ies); US = United States; VCR = vincristine; VXLD = vincristine, dexamethasone, PEG-asparaginase, and daunorubicin; WM = Waldenström's macroglobulinemia
 Studies 2011-003 (ENDEAVOR) and 2012-005 (CLARION) are co-sponsored by Amgen and Ono Pharmaceutical Co, Ltd. in Japan and is sponsored solely by Amgen in other participating countries. All other studies are sponsored solely by Amgen.
 All studies were open-label.

^aUnless otherwise noted, carfilzomib was administered in 28-day cycles on days 1, 2, 8, 9, 15, and 16 until progressive disease. Stepped-up dosing was allowed on cycle 1 day 8 for Studies PX-171-009 (ASPIRE), PX-171-011 (FOCUS), 2011-003 (ENDEAVOR), PX-171-007, 2011-002, CFZ001, CFZ002, 20140242 (CFZ005), 20140355 (A.R.R.O.W.), 20160275 (CANDOR); on cycle 2 day 1 for Studies PX-171-002 – Part 2, PX-171-003 – Part 2 (A1), PX-171-004 – Part 2, and PX-171-005. Where applicable, and unless otherwise noted, dexamethasone was administered at 40 mg weekly.

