7.7.1.1 Primary Analysis

In response to the anticipated variations in the sample sizes and data variables collected for these 13 clinical trials, there will be a primary analysis and a subsequent sensitivity analysis to avoid the introduction of extra-variation to the pooled data. The primary analysis will consist of all studies that meet the eligibility criteria with an adequate sample size of at least 20 subjects and at least 80% completeness of data for each variable in [List 1](#) (Table 2). This yields 5 clinical trials for K monotherapy totaling 564 subjects and 6 clinical trials for Kd totaling 1,199 subjects.

Table 2. Clinical Trials for Primary Data Analysis

K27 (540 subjects)	K56 (24 subjects)	Kd27 (583 subjects)	Kd56 (616 subjects)
20140119 (78 subjects)	20130393 (24 subjects)	20140355 (235 subjects)	20160275 (153 subjects)
20140118 (200 subjects)		20140242 (123 subjects)	20130398 (463 subjects)
20130396 (157 subjects)		20140120 (20 subjects)	
2011-002 (105 subjects)		2011-002 (205 subjects)	

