For the secondary and exploratory endpoints, each propensity score analysis will compare the efficacy (Hazard Ratio (HR)(CI) for PFS and Odds Ratio (OR)(CI) for ORR) and safety outcomes (Risk Ratio (RR)(CI)) overall and in subgroups determined by the clinical parameters from [List 1](#) (covariates). Based on the results, the favorable versus unfavorable effects of Kd27 versus Kd56 and K27 versus Kd27 will be summarized. The comparison of K27 versus K56 will not be included due to the limited sample size of the K56 cohort.

For further details, please refer to Section 9.5 and 9.6 of the SAP.

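### The matched K27 versus Kd27 safety risk ratio can partly reflect trial differences and a 12-cycle limit that applies to half of K27 and no Kd27

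*Protocol*

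**What the plan says.** Protocol section 6.3 makes K27 versus Kd27 the exploratory comparison. Section 7.2.2 says that all List 1 variables "will be included in the propensity score model (logistic regression model) with the dosing regimen as the binary response". It then extends the greedy 1:1 nearest-neighbour match, without replacement and with a caliper of 0.1 standard deviations on the logit, to this pair: "Same method will be used to create a propensity score matched samples for subjects with Kd27 or K27". List 1 contains year of treatment initiation but not trial, and section 7.2.2 states no restriction to pairs from the same trial.

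Table 2 (section 7.7.1.1) gives the primary analysis set. Study 2011-002 is the only trial in both the K27 column (105 subjects) and the Kd27 column (205 subjects).

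Table 1 (section 7.7.1) describes the K27 parts of 20140119 and 20140118 with the note "10 min) up to 12 cycles". No Kd27 trial in Table 2 carries such a note. Footnote a to Table 1 says that, unless otherwise noted, carfilzomib was given "on days 1, 2, 8, 9, 15, and 16 until progressive disease".

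Section 7.7.2.4 says the propensity analyses will compare "safety outcomes (Risk Ratio (RR)(CI)) overall and in subgroups", with a hazard ratio for PFS and an odds ratio for response. The same section plans exposure-adjusted incidence rates in addition. Section 7.9.2 concedes that unobserved covariates cannot be balanced and that unmatched subjects are lost. It then says that no better method exists for handling population differences among the trials.

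**The concern.** How long a subject could be treated, and so for how long treatment-emergent events could accrue, is set by the trial. It is not a baseline characteristic. Two subjects with identical List 1 values can be paired even though one was in a trial that ended treatment at cycle 12 and the other in a trial that treated until progression. If trials with a fixed limit sit almost entirely on one side, a crude risk ratio compares events over unequal windows, and good covariate balance will not show this. Other trial-level differences enter in the same way.

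At stake is how the comparison is read. Section 7.7.2.4 will summarise the relative advantages of K27 and Kd27 from these contrasts, and section 7.9.2 offers them as the way to learn more about monotherapy. An excess of events on Kd27 could be read as a cost of adding dexamethasone when part of it is longer observation on treatment.

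**Working it through.** **1. Table 2 counts reproduce.**
- K27: 78 + 200 + 157 + 105 = 540, as stated.
- Kd27: 235 + 123 + 20 + 205 = 583, as stated.

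**2. Share from trials with a listed 12-cycle limit.**
- K27: (200 + 78)/540 = 278/540 = 51.5%.
- Kd27: 0/583.
- Sensitivity set (Table 3), which adds 20140122 with the same limit: K27 285/559 = 51.0%; Kd27 3/586 = 0.5%.

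**3. Availability of same-trial partners, primary set.**
- 2011-002 supplies 105/540 = 19.4% of K27 and 205/583 = 35.2% of Kd27.
- The other 540 − 105 = 435 K27 subjects (80.6%) can be paired only with a Kd27 subject from a different trial.

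**4. How large the distortion of a crude risk ratio could be.** The protocol does not give time on treatment or event incidence, so these are assumptions:
- time on treatment without a limit is exponential with the same median m in both regimens;
- the event hazard h is constant while on treatment and identical in both regimens, so there is no true effect;
- the incidence without a limit is 10%;
- the matched K27 sample keeps the 51.5% share.

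The limit is T = 12 × 28 = 336 days = 48 weeks, or about 11.04 months. Let λ = ln 2/m, and choose h so that h/(h + λ) = 0.10. A subject under the limit then has incidence 0.10 × [1 − exp(−(h + λ)T)]. With c = 278/540,

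spurious RR (Kd27/K27) = 1 / [1 − c × exp(−(h + λ)T)].

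The corresponding ratio of mean exposure is 1 / [1 − c × exp(−λT)].

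| Assumed median m (months) | Still on treatment at T | Mean exposure ratio Kd27/K27 | Spurious RR |
|---|---|---|---|
| 3 | 7.8% | 1.04 | 1.03 |
| 6 | 27.9% | 1.17 | 1.14 |
| 9 | 42.7% | 1.28 | 1.25 |
| 12 | 52.9% | 1.37 | 1.34 |

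Example for m = 6: λ = 0.1155, h + λ = 0.1155/0.9 = 0.1284, exp(−0.1284 × 11.04) = 0.242, and 1/(1 − 0.515 × 0.242) = 1.14.

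Under these same assumptions an event rate per unit of exposure would show no difference.

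**5. Precision of a comparison within 2011-002.** With n matched pairs and incidence p in both groups, the 95% CI multiplies and divides the risk ratio by exp(1.96 × √[2(1 − p)/(p n)]). The incidences are assumed.

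| p | n = 105 (most possible in 2011-002) | n = 540 (most possible overall) |
|---|---|---|
| 20% | 1.72 | 1.27 |
| 10% | 2.25 | 1.43 |
| 5% | 3.25 | 1.68 |

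**The case against.** Much of the other side stands.

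- **Exposure is not ignored.** Section 7.7.2.4 plans exposure-adjusted incidence rates expressly for differences in treatment duration, and section 7.7.2.3 describes duration and cumulative dose by group. A reader might infer that the plan leaves exposure unhandled; it does not. What remains is that the propensity safety contrast is named as a risk ratio, that the rates assume a constant event rate, and that they do nothing for PFS. The protocol does not say whether the rates use matched data.
- **2011-002 is not a randomised control that the plan throws away**, though a reader might infer that. Table 1 lists it as a single-arm expanded access study with safety as its only objective. Section 7.2.1.1 assigns dexamethasone status by what the subject received. Both of its groups stay in the matching pool. A comparison within it removes trial differences but not confounding by indication. It cannot help the 80.6% of K27 with no same-trial partner, and nothing shows that its PFS or response data are usable.
- **PFS.** A reader might infer that stopping at cycle 12 makes K27 PFS look worse. An effect is possible, but the protocol does not say what happened to progression-free subjects after cycle 12, and each trial's PFS rules sit in its own SAP.
- **Size.** At short times on treatment the distortion is slight, and even 540 pairs would give a confidence factor of 1.43 at 10% incidence.
- **Year of treatment initiation** may partly stand in for trial. It cannot carry a stopping rule, and the protocol gives no trial dates by which to judge it.
- **The comparison is exploratory and descriptive**, and details are deferred to SAP section 9.5.2.1, which is not shown. The score's variables, the matching method, the effect measure and the statement that no better method exists are, however, fixed in the protocol.

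**Conclusion.** The point holds as a risk of moderate size in an exploratory comparison. The method as stated cannot separate dexamethasone from trial and treatment window: 51.5% of K27 against none of Kd27 comes from trials with a listed 12-cycle limit, and at least 80.6% of K27 subjects can be paired only across trials. The crude matched risk ratio could be pushed up for Kd27 by about 3% at an assumed median of 3 months on treatment and by about 34% at 12 months. This assumes a 10% incidence, a constant hazard, exponential time on treatment and no true difference. Which end applies cannot be told from the protocol. The documents do not support the stronger reading that trial and exposure differences will be mistaken for a dexamethasone effect.

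The general statement in section 7.9.2 that no better method exists goes too far here. A common 12-cycle window and a comparison within one trial are both available from data in hand, and each removes a specific source of bias, though neither resolves confounding by indication.

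**What to change.** 1. Beside the planned matched risk ratio for K27 versus Kd27, report a safety contrast that counts adverse events in both groups only through cycle 12 plus the treatment-emergent window. Report the 48-week Kaplan-Meier PFS estimate next to the hazard ratio.
2. Match 2011-002 subjects within 2011-002 and report that comparison as a supportive sensitivity analysis, mainly for safety. State that it has at most 105 pairs, that dexamethasone is not shown to be randomised there, and that precision is limited (confidence factor about 1.7 at an assumed 20% incidence and 2.25 at 10%).
3. In section 7.9.2, name trial and the 12-cycle limit as limitations of this comparison, and qualify the statement that no better method exists.

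The cost is some wording and a few extra tables from data already held. Late events drop out of the truncated contrast only; they remain in the planned analyses.

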7.2.3 Baseline Period

The baseline period is defined as the period from screening up to the time before the first dose of protocol-specified treatment was given, during which the data obtained for each variable or covariate in [List 1](#). If multiple values were obtained during this time period, then the most recent value prior to the first dose of protocol-specified treatment will be used as the baseline parameter.

7.3 Variables

Selection of current treatments depend on a plethora of clinical parameters that vary in important and might affect the choice of K regimen for a particular patient. Given that the benefit-risk assessment is a cornerstone of decision making in medicine, and benefit-risk assessment is based upon efficacy outcomes and safety outcomes ([Reaney et al, 2019](#); [Curtin et al 2011](#)), special consideration will be given to clinical parameters known to impact efficacy and safety outcomes. Further consideration will be given to those clinical parameters that may be unique to efficacy and safety outcomes in those treated with carfilzomib. Specified below are the clinical parameters for analysis (List 1) for efficacy outcomes such as progression-free survival (PFS) and objective response rate and safety outcomes such as fatalities, grade 3 or higher AEs of special interest for carfilzomib, and serious AEs of special interest for carfilzomib. Variables common to both efficacy and safety outcomes are listed first. Further details are specified in the SAP.

List 1. Planned Variables to be Analyzed that May Inform the Choice of Carfilzomib Dosing Regimen

Variables for efficacy outcomes	Variables for safety outcomes
Age	Age
Gender	Gender
Race	Race
Ethnicity	Ethnicity
Body mass index	Body mass index
ECOG* performance status	ECOG performance status
Creatinine clearance	Creatinine clearance
Time from initial diagnosis	Diabetes
Stage of disease (International Staging System)	Dyslipidemia/hypercholesterolemia
Lactate dehydrogenase	Hypertension
Presence of plasmacytoma	Left ventricular hypertrophy
Number of prior lines of therapy	Chronic kidney disease
Prior stem cell transplant	Coronary artery disease
Prior exposure to lenalidomide	Year of treatment initiation
Prior exposure to bortezomib	
Refractory to lenalidomide	
Refractory to bortezomib	
Refractory to last treatment	
Time from last relapse or last treatment	
Year of treatment initiation	

* Eastern Cooperative Oncology Group

7.3.1 Rationale of Variables Pertaining to Subject Characteristics: Age, Gender, Race, Ethnicity, Body Mass Index, ECOG Performance Status, Creatinine Clearance

Established prognostic patient characteristics, not only for myeloma but the majority of oncological diseases, include age ([Brinthen S et al, 2013](#); [Chretien M-L et al, 2014](#); [Qian J et al, 2017](#);) and performance status ([ECOG-ACRIN Cancer Research Group, 2020](#); [Jang RW et al, 2014](#)). While body habitus, as measured via body mass index, is a known MM risk, it is potentially a prognostic risk ([Beason et al, 2013](#); [Tamayo RR et al, 2014](#)). Given the discrepancy of the incidence of MM and outcomes between genders ([Boyd KD et al, 2011](#)) and among different races and ethnicities ([Fillmore NR et al, 2019](#); [Waxman AJ et al, 2010](#)), these demographics were deemed important to include. For decades, renal dysfunction has been part of the CRAB criteria (acronym for

hypercalcemia, renal failure, anemia, and bone disease) for end-organ damage to diagnosis MM ([Rajkumar et al, 2014](#)). With at least 50% of patients with MM having renal dysfunction at presentation due to the proteins secreted by the malignant cells ([Yaday et al, 2016](#)), creatinine clearance is a recommended diagnostic evaluation per NCCN guidelines and serves an important eligibility criterion in MM clinical trials ([Bringham S et al, 2013](#); [National Comprehensive Cancer Network Clinical Practice \(NCCN\) Guidelines in Oncology, 2020](#)).

7.3.2 Rationale of Variables Pertaining to Subject Co-morbidities: Diabetes, Dyslipidemia/hypercholesterolemia, Hypertension, Left Ventricular Hypertrophy, Chronic Kidney Disease, Coronary Artery Disease

Additional variables will include those that are associated with baseline co-morbidities, which are evolving prognostic variables and appear to influence treatment patterns in RRMM ([Kleber et al, 2011](#)). Notable ones are cardiac and renal comorbidities, as these may be aggravated not only from the MM itself, but also from disease treatments, including carfilzomib ([Ritts et al, 2016](#); [Bruno et al, 2019](#)). These may be overlapping as renal insufficiency and have been shown to increase the risk of cardiovascular disease up to four-fold ([Gansevoort et al, 2013](#)). Diabetes, dyslipidemia or hypercholesterolemia, and hypertension are known to be more prevalent in those with multiple myeloma at the time of diagnosis compared to age- and gender-matched healthy individuals. Specifically, the respective prevalence for diabetes, dyslipidemia, and hypertension is approximately 27%, 41%, and 53% for those with MM at the time of diagnosis compared to approximately 11%, 32%, and 41% for the matched healthy individuals ([Markus et al, 2020](#)). Other baseline comorbidities of left ventricular hypertrophy, coronary artery disease, and chronic kidney disease are also important covariates to include given that carfilzomib is associated with cardiac and renal toxicity and have been previously explored with need for further investigation (Carfilzomib Investigator's Brochure, 2019; Bruno et al, 2019; [Dimopoulos et al, 2017](#)). To date, there are still no known predictive factors for such adverse events and the carfilzomib mechanism causing toxicity remains unclear.

7.3.3 Rationale of Variables Pertaining to Disease Characteristics: Time From Initial diagnosis, Stage of Disease, Lactate Dehydrogenase, Presence of Plasmacytoma, Number of Prior Lines of Therapy, Prior Stem Cell Transplant, Prior Exposure to Lenalidomide, Prior Exposure to Bortezomib, Refractory to Lenalidomide, Refractory to Bortezomib, Refractory to Prior Treatment, Time From Last Relapse of Last Treatment

Prognostic disease characteristics have been identified by the International Staging System (ISS) and Revised-ISS, which as of 2015 the latter consists of albumin and β 2 microglobulin from the ISS, along with the addition of lactate dehydrogenase (LDH), and chromosomal abnormalities detected by interphase fluorescent in situ hybridization (iFISH) (Greipp et al, 2005; Palumbo A et al, 2015). ISS and LDH will be evaluated as separate covariates. Another important and frequent complication at presentation is the presence of extramedullary plasmacytomas, which tend to be resistant to conventional treatments and seems to be biologically distinct from high-risk molecular and histological features (Chen HF et al, 2012; Sevcikova S et al, 2019). One of the most important disease characteristics in the RRMM setting is the duration of disease control, which can be evaluated by time from initial diagnosis and time from last relapse/treatment (Kumar SK et al, 2018; Durie BGM, 2018; Lancman G et al; 2017; Dingli et al, 2017). The duration of disease control is likely determined by the disease biology, but may also be determined by previous treatment and drug exposures. With further guidance from recent literature review and input from subject matter experts regarding prognostic baseline clinical parameters in rapidly evolving RRMM treatment landscape, prior stem cell transplant, prior exposure and/or refractoriness to bortezomib, prior exposure and/or refractoriness to lenalidomide, and refractoriness to prior treatment are included as covariates (Dingli et al, 2017; Dimopoulos et al, 2015; Barlogie et al, 2011; Rajkumar et al, 2001).

7.3.4 Rationale of Variable Pertaining to Treatment Patterns: Year of treatment initiation

It is recognized that the implementation of these Amgen acquired or sponsored clinical trials spanned nearly a decade, whereby the understanding of the myeloma disease greatly has improved and the clinical development of K proceeded from preclinical to robust clinical studies. As the RRMM treatment combinations and patterns are dynamic, an additional clinical parameter to consider is the year of treatment initiation.

